## 10.2 STATISTICAL HYPOTHESES

The primary hypothesis is that patients' report of pain (and/or use of pain medication) will be 2.8 points lower on the pain scale (0-10) while on the resveratrol than while on placebo.

The secondary hypothesis for this study states that the change in self-reported HRQoL from the start of the study period to the end will be different in PSACH patients during the period they are on resveratrol compared to when they are on placebo.

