## PROTOCOL SUMMARY

[figure not shown]
Title:	Trial of Resveratrol for Pseudoachondroplasia Pain
Précis:	This is a cross over designed study to determine if self-administered oral resveratrol (90 days) can dampen joint pain for individuals with pseudoachondroplasia compared to placebo (90 days) as measured by daily pain logs.
Objectives:	To determine if resveratrol reserveage liquid lessens joint pain in individuals with pseudoachondroplasia.
Endpoint	Self-reported pain as ascertained by a 11-point pain scale from 0 to 10.
Population:	Pseudoachondroplasia patients aged 18 to 70 yrs (details below)
Phase:	IIA ("proof of concept" study)

**Number of Sites enrolling participants:** 1  
**Description of Study Agent :** Resveratrol Reserveage liquid super berry blend 225 mg + Pro-longevity factors blend 130 mg including **125 mg trans-resveratrol**

**Study Duration:** 5 yrs  
**Participant Duration:** 210 days

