## 10 STATISTICAL CONSIDERATIONS

## 10.1 STATISTICAL AND ANALYTICAL PLANS

The primary outcome (change in pain between baseline and monthly pain average score) will be scored using the the Numeric Pain Rating Scale. Based on prior studies that utilized these scales, a difference of at least 2 units on the 11-point scale are considered to be a reflection of a true change in pain. Median and mean monthly pain will be compared. The pain score on each day of month one will be averaged to obtain the average pain score for month one, and the same will be done for months two and three, and each of the monthly average scores will be compared to baseline. For the secondary outcome measure, baseline HRQoL will be compared to the 30, 60, and 90 day HRQoL scores.

Data from the daily pain logs and the monthly HRQoL assessments will be used to evaluate changes in outcomes within each intervention period stratified by study drug. The analysis will be performed within the framework of the 2x2 crossover study design. Baseline characteristics (demographic and clinical) will be tabulated. Exploratory analyses will be performed to assess differences in outcomes as stated above after further stratification by gender.

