### 10.5 SAMPLE SIZE

Although studies haven't quantified pain variability in PSACH, other studies have utilized a pain VAS and have reported standard deviation (SD) of the difference between scores for the same patient of about 10-15 on a 1-100 scale. In addition, previous research by one of the investigators has suggested that a strong placebo effect can be present in studies using the pain VAS at a magnitude of about 20 on a 1-100 scale. Assuming a similar degree of variability in our study population and considering the placebo effect as reported, with a sample size of 30 participants at a Type I error rate of 5%, the minimal detectable difference would be 2.8 units at a SD of 10 and power of 80%, 4.25 at a SD of 15 and power of 80%, 3.3 at a SD of 10 and power of 90%, and 4.9 at a SD of 15 and power of 90%. Considering that there are about 300 potential patients that can be approached through the "Little People of America" support group and the Facebook PSACH group, we should be able to recruit into the study at least half of those highly motivated and invested individuals. We should be able to achieve our sample size of 30 patients for this study, even assuming a considerably high 33% attrition rate. We will screen 60 to enroll 30.

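### The 2.8-point effect in the primary hypothesis (0-10 scale) matches only a detectable difference worked out on a 1-100 scale, so it has no derivation in the trial's own units

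*Combined protocol and SAP*

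**What the plan says.** The Protocol Summary fixes the endpoint scale: "Self-reported pain as ascertained by a 11-point pain scale from 0 to 10". Section 4.2.1 uses the same 0-10 numeric rating scale (NRS).

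Section 10.2 predicts that pain "will be 2.8 points lower on the pain scale (0-10) while on the resveratrol than while on placebo". It gives no reason for the value and refers to no other section.

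Section 10.5 borrows its variability from other studies that used a visual analogue scale, with a "standard deviation (SD) of the difference between scores for the same patient of about 10-15 on a 1-100 scale". It puts the placebo effect at about 20 on that same scale. For 30 participants and a 5% type I error it then says that "the minimal detectable difference would be 2.8 units at a SD of 10 and power of 80" per cent, and gives three further values: 4.25 (SD 15, 80% power), 3.3 (SD 10, 90%) and 4.9 (SD 15, 90%). None of these is converted to the 0-10 scale.

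Section 10.1 names one other magnitude, on the endpoint's own scale: "a difference of at least 2 units on the 11-point scale are considered to be a reflection of a true change in pain".

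On sample size, sections 4.1 and 10.5 say 30 participants, while section 10.6.1 says one hundred will be enrolled.

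**The concern.** A detectable difference carries the units of the SD that produced it. The 2.8 in section 10.5 goes with an SD of 10 on a 1-100 scale, so it is 2.8 units out of about 100. Section 10.2 gives the same number on a scale one tenth as long. No other origin for 2.8 appears anywhere.

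At stake is the link between the hypothesis and the sample size. A reader of section 10.2 would suppose that 30 participants were chosen to detect 2.8 NRS points with 80% power. Section 10.5 shows nothing of the kind. The result will also be read against what the plan said it expected, and on the NRS the two sections imply magnitudes a factor of ten apart.

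**Working it through.** **Inputs.** Hypothesised effect 2.8 on 0-10 (10.2). SD of within-patient differences 10 to 15 on 1-100, N = 30, alpha 5% (10.5). Threshold of 2 units on 0-10 (10.1). Enrolment of 100 (10.6.1). Sidedness is not stated; two-sided is assumed.

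**Step 1: can the section 10.5 figures be on 0-10?** Differences between two scores on 0-10 lie between -10 and +10, so their SD cannot exceed 10 (apart from a small-sample correction). An SD of 10 would need half the patients at +10 and half at -10. The companion SD of 15 is impossible. The figures are therefore on 1-100, as the section says.

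**Step 2: convert.** 2.8 / 10 = 0.28 NRS points (2.8 / 9.9 = 0.283 if the 1-100 range is taken literally). Ratio to section 10.2: 2.8 / 0.28 = 10. The SDs become 1.0 to 1.5 and the placebo effect about 2.

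**Step 3: try to reproduce the printed values.** For a paired comparison the normal approximation is MDD = (z for alpha/2 + z for power) × SD / √N. At N = 30, SD 10 and 80% power this is (1.960 + 0.842) × 10 / √30 = 5.12, not 2.8. The exact version uses the noncentral t with N - 1 degrees of freedom. On the 1-100 scale it gives:

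| SD, power | Printed | N = 30 (t) | N = 100 (t) |
|---|---|---|---|
| 10, 80% | 2.8 | 5.29 | 2.83 |
| 15, 80% | 4.25 | 7.94 | 4.24 |
| 10, 90% | 3.3 | 6.12 | 3.27 |
| 15, 90% | 4.9 | 9.19 | 4.91 |

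All four printed values come back at N = 100 and none at N = 30. Inverting the normal formula for 2.8 gives N = 100.1. A one-sided test at N = 30 gives 4.65 for the first row. One-sided testing would imply an N of about 77 to 80, which the plan nowhere mentions. Changing the variance factor (SD × √(2/N) or SD / √(2N)) does not give 2.8 at N = 30 either.

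**Step 4: detectable differences in NRS points at N = 30.** Dividing the N = 30 column by ten gives 0.53 (SD 1.0) and 0.79 (SD 1.5) at 80% power, and 0.61 and 0.92 at 90% power.

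**Step 5: compare with the hypothesis.** 2.8 / 0.53 = 5.3 and 2.8 / 0.79 = 3.5. The hypothesised effect is 3.5 to 5.3 times the 80%-power detectable difference at N = 30.

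**Step 6: would 0.28 serve as the target?** At N = 30 the power for 0.28 points is 32% with SD 1.0 and 17% with SD 1.5. It is also 0.28 / 2 = 14% of the section 10.1 threshold. It would not.

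**The case against.** The strongest reply is that 2.8 points on 0-10 was a deliberate, optimistic hypothesis. It is a possible value, it exceeds the 2-unit threshold, and nothing says that it was taken from section 10.5. That stands in part: copying is an inference. It is a strong one, because the number is identical and no other rationale is given. The reply does not remove the defect, though. A deliberate 2.8 would have no stated basis, and the power statement would not relate to it.

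Three stronger readings are tempting, and the documents do not support them.

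- A reader might infer that the plan has three contradictory targets (2.8, about 0.28 and 2 NRS points), so that one result could be declared both a success and a failure. These are different quantities: a hypothesised effect, a detectable difference and a threshold for real change. A hypothesis may properly lie above the other two. No section makes any of them a success criterion. The analysis in section 10.4.1 is a mixed model that does not use 2.8, and section 10.4.7.2 rules out an interim efficacy analysis.
- A reader might argue that 2.8 NRS points cannot have been the target because, with SDs of 1.0 to 1.5, only 4 to 5 participants would give 80% power. By the same test the 2-unit threshold would need only 5 to 7, so the argument does not separate the two. The SDs are also borrowed; section 10.5 says that variability in this condition has not been quantified.
- A reader might conclude that 2.8 should simply become 0.28. Steps 3 and 6 show why not.

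**Conclusion.** The point holds as a mismatch of scale and an unsupported target. Section 10.2 states 2.8 on 0-10; the only derivation of 2.8 is on 1-100, where it equals about 0.28 NRS points. The gap is tenfold against the printed figure, and 3.5- to 5.3-fold against the 80%-power detectable difference recomputed for 30 participants. Carry-over without conversion is the likely cause, not a documented one.

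No test, estimate or dataset changes. The harm is to the stated primary hypothesis, to the justification of the sample size and to how the result is read.

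The recomputed values assume two-sided 5% testing, a paired t comparison, 30 participants contributing both periods, and that the borrowed SD of 10 to 15 applies to the resveratrol-placebo difference. The tenfold mismatch of scale needs none of these assumptions.

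**What to change.** **Section 10.2.** Remove the 2.8-point figure. State the hypothesis as lower mean NRS pain on resveratrol than on placebo, with the estimate and its confidence interval read against the 2-unit threshold in section 10.1. Alternatively, give a target justified on the 0-10 scale. If the 2-unit threshold is kept as the yardstick, say why it suits this population: the titles of the two references cited for it concern children, one of them acute pain, and the trial enrols adults aged 18 to 70. The sentence in 10.2 also covers use of pain medication; the rewrite should deal with that openly and not drop it unremarked.

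**Section 10.5.** Express the SDs (about 1.0 to 1.5), the placebo effect (about 2) and the detectable differences in NRS points, and state the sidedness. Recompute at the actual N instead of only dividing by ten. At N = 30, under the assumptions above, the values are 0.53 and 0.79 at 80% power and 0.61 and 0.92 at 90% power (SD 1.0 and 1.5 respectively).

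**Section 10.6.1.** Reconcile the enrolment of one hundred with the 30 in sections 4.1 and 10.5, because the printed detectable differences fit the former.

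The cost is revised wording in 10.2, one short recalculation in 10.5 and a consistent sample size across the sections. Data collection and the analysis model stay as they are. The change should be made before unblinding, so that the yardstick is not chosen after the result is known.

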## 10.3 ANALYSIS DATASETS

The dataset analyzed will be comprise of demographic and clinical information obtained from the patient, the pain scores obtained from the pain and HRQoL instruments described above. The database will be maintained by the study coordinator and will be password-protected and stored on the secure and HIPAA-compliant University of Texas Health Science Center's zone 100 network. It will be accessible only to the study staff.

## 10.4 DESCRIPTION OF STATISTICAL METHODS

### 10.4.1 GENERAL APPROACH

Multilevel mixed-effects models will be utilized to assess the data while accounting for the lack of independence of data obtained from multiple time-points while considering the initial (baseline) outcome scores, type of intervention (placebo vs. resveratrol) and the sequence of intervention (placebo first, then resveratrol, or vice versa). This analysis will be performed using STATA (v.14, College Station, TX). Exploratory analyses after stratification by subject's gender will also be performed.

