### 10.4.2 ANALYSIS OF THE PRIMARY EFFICACY ENDPOINT(S)

A baseline pain assessment will take place at the first visit (day 0). Pain will then be ascertained daily (including during the "washout" period between the two intervention periods) through a daily pain log kept by participants. The pain logs will be requested from participants at each follow-up visit and at the end of each month in the treatment periods, and data from the pain logs will be compiled and analyzed at the start and end of each of the two treatment periods (on days 0, 90, 120, and 210). Each of these scores will then be entered as raw values for each subject if the parameter distribution is non-normal, ranked values will be used as units of analysis.

The primary endpoint will be change in pain score between baseline and monthly average pain score. The pain score on each day of month one will averaged to obtain the average pain score for month one, and the same will be done

for months two and three, and each of the monthly average scores for resveratrol and placebo periods will be compared to baseline.

In an extreme condition, if a sufficiently large proportion (>30%) of the study subjects experience no pain (a score of 0), zero-inflated negative binomial models will be utilized to analyze the data while considering the individuals that report no pain.

---

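### Section 10.4.1 names no period effect, so a shift in pain between periods would bias the drug estimate if sequence sizes differ and change is taken from day 0

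*Combined protocol and SAP*

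**What the plan says.** Section 10.4.1 describes multilevel mixed-effects models that allow for repeated measurements and take account of the initial score, "type of intervention (placebo vs. resveratrol) and the sequence of intervention (placebo first, then resveratrol, or vice versa". Section 10.4.9 adds only that the models handle the repeated measurements. Section 10.1 states: "The analysis will be performed within the framework of the 2x2 crossover study design". It names no terms.

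The baseline for period 2 is not settled. Section 10.4.2 says "A baseline pain assessment will take place at the first visit (day 0" and that "each of the monthly average scores for resveratrol and placebo periods will be compared to baseline", which reads as one day-0 baseline for both periods. The same section has the logs "compiled and analyzed at the start and end of each of the two treatment periods (on days 0, 90, 120, and 210", and 10.1 says the data will be used to "evaluate changes in outcomes within each intervention period stratified by study drug". Either could point to day 120 as the baseline for period 2.

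Section 10.4.3 applies the same models to HRQoL. Sections 7.1.1 and 10.6.1 describe randomization to two sequences without an allocation ratio or blocking, and 10.6.1 says dropouts are not replaced.

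**The concern.** In a two-period crossover each participant receives one treatment early and the other late. Anything that moves pain over the 210 days (a fading placebo response, season, disease course, changing use of the log) enters each participant's resveratrol-minus-placebo difference. Its sign is opposite in the two sequences. A period term removes it. A sequence term cannot, because it compares participants with one another and drops out of the within-participant difference. A day-0 baseline drops out for the same reason.

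Two things are at stake. If the sequences differ in size, the shift does not cancel and part of it is attributed to the drug. If they are equal, it cancels from the estimate but stays in the residual variation and widens the reported SE relative to a model with period.

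**Working it through.** **Inputs.** From 10.5: N = 30, alpha 5%, and an SD of the within-patient difference of 10-15 on a 1-100 scale. The documents give no period shift. I assume 2, 5 and 10 on that scale (0.2, 0.5 and 1.0 points on 0-10), which is 10%, 25% and 50% of the placebo effect of about 20 cited in 10.5.

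**The plan's own figure.** Section 10.5 gives a minimal detectable difference (MDD) of 2.8 at SD 10 and 80% power. With N = 30 and a two-sided test, (1.960 + 0.842) × 10/√30 = 5.11, or 5.29 with the t distribution. The stated 2.8 corresponds to N = 100: 2.802 × 10/√100 = 2.80. That is a separate matter. I use 5.29 below as the reference for N = 30.

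**Bias.** Let τ be the drug effect and π the shift (period 2 minus period 1). The expected resveratrol-minus-placebo difference is τ + π for placebo-first participants (n1) and τ − π for resveratrol-first participants (n2). Without a period term the estimate is the mean over all participants, so

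bias = π × (n1 − n2)/N.

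| Split | Shift 2 | Shift 5 | Shift 10 |
|---|---|---|---|
| 15:15 | 0 | 0 | 0 |
| 18:12 (6/30) | 0.4 | 1.0 | 2.0 |
| 20:10 (10/30) | 0.7 | 1.7 | 3.3 |

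If 10% of 30 were lost, all from one sequence, the split would be 15:12 and the bias at shift 10 would be 10 × 3/27 = 1.1. Simulation with fixed splits at SD 10 and shift 10 gave a bias of 1.99 at 18:12 and 3.30 at 20:10 without period, and 0.01 and 0.04 with it.

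If randomization is 1:1 and unblocked (an assumption), the chance of 18:12 or worse is 0.36 and of 20:10 or worse 0.10. Averaged over such splits the bias is zero.

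**Reported SE, one value per period.**

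- Without period: √{[SD² + π² × 4n1n2/(N(N − 1))]/N}
- With period: (SD/2) × √(1/n1 + 1/n2)

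At 15:15, SD 10 and shift 10: √[(100 + 100 × 900/870)/30] = 2.604, against 5 × √(2/15) = 1.826, a ratio of 1.43.

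| SD (15:15) | Shift 2 | Shift 5 | Shift 10 |
|---|---|---|---|
| 10 | 1.02 | 1.12 | 1.43 |
| 15 | 1.01 | 1.06 | 1.21 |

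If instead three monthly averages per period are modelled and all the noise is month-level, the ratios at SD 10 are only 1.00, 1.03 and 1.10. With unequal splits the ratio can fall below 1: at 20:10, SD 10 and shift 2 it is 1.859/1.936 = 0.96.

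**Error rate and power, one value per period, SD 10.** At shift 10, type I error without period is about 0.6% at 15:15, 4.5% at 18:12 and 17% at 20:10. Averaged over unblocked splits it is 5.0%. At 15:15, power for a true difference of 5.3 is 79%, 73% and 50% at shifts of 2, 5 and 10, against 80% with period.

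**Against the plan's own effects.** Section 10.1 states that "a difference of at least 2 units on the 11-point scale are considered to be a reflection of a true change in pain", and 10.2 hypothesizes that pain "will be 2.8 points lower on the pain scale (0-10) while on the resveratrol than while on placebo". These are 20 and 28 on the 1-100 scale. A bias of 2.0 is 2.0/20 = 10% or 2.0/28 = 7% of them, and power for either stays above 99% at shift 10.

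**The case against.** The best defence is that 10.4.1 does not claim to be a full list, and that an analysis within the 2x2 crossover framework would ordinarily include period. That may be the intention, but the one explicit list leaves it out and no other sentence supplies it.

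A second defence is that day 120 may be the baseline for period 2. That would remove any shift already present by then, though not a later one. It is more plausible for HRQoL, where 10.4.3 collects a score at the start of the second period. This stands, and it is why the point is conditional on a day-0 baseline.

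Third, the harm is hypothetical. The placebo effect in 10.5 is a response size, not a difference between periods, and the fractions of it used here are assumptions. The 17% error rate needs a full 1-point shift together with a 20:10 split. If the hundred participants of 10.6.1 were randomized instead of 30, chance imbalance would be proportionally smaller. Under unblocked 1:1 allocation the SD of (n1 − n2)/N is 1/√N, so a one-SD imbalance at shift 10 gives 10/√30 = 1.8 at N = 30 and 10/√100 = 1.0 at N = 100. All of this stands.

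A reader might infer more, namely that with equal sequences the SE is simply too large. The documents do not support that. They analyse three monthly averages per period and do not specify the random effects. If only a participant effect is fitted and half the difference variance lies at participant-by-period level (both assumed), the mean SE at 15:15 and SD 10 without period is 1.42, 1.47 and 1.63 at the three shifts, against a true spread of about 1.83. That SE is too small. Only the relative statement holds: the SE exceeds that of the same model with period.

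**Conclusion.** The point holds as a conditional weakness that is cheap to remove. The stated terms cannot absorb a period shift. If there is one and change is taken from day 0, a trial with unequal sequences carries a bias of shift × (difference in sequence sizes)/N: 2.0 at 18:12 and 3.3 at 20:10 for an assumed shift of 10 and N = 30. The bias averages to zero over 1:1 randomization without differential dropout, but the trial will have a single realized split. With equal sequences the cost is a relatively larger SE, by 2% to 43% at SD 10 with one value per period and by less if month-level noise dominates.

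It would not be right to conclude that this trial's result will be biased. No shift is documented, and without one nothing is lost. For differences of 2 or 2.8 points the effect is small. It matters mainly for the false-positive rate and for true differences near 5.3 on 1-100.

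**What to change.** In 10.4.1, and by reference in 10.4.3, add a fixed effect for period (first or second) alongside treatment, sequence and baseline. State whether change in period 2 is measured from day 0 or day 120. This takes two sentences and one degree of freedom. With no shift, the MDD at N = 30 and SD 10 goes from 5.29 to 5.30 at 15:15, and to 5.41 at 18:12.

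A separate, secondary point concerns the random effects. Because three monthly averages per period are analysed, either include a participant-by-period random effect or analyse one summary value per participant per period. If a participant-only effect were fitted and half the difference variance were at participant-by-period level (assumed, SD 10), type I error would be about 13% even with the period term. Without it, averaged over unblocked splits, it would be 13.6%, 16.1% and 21.8% at shifts of 2, 5 and 10. With period and participant-by-period together it is 5.1%. The cost is one variance component and an honest SE of 1.81 in place of 1.41, where the true spread is 1.83.

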### 10.4.2 ANALYSIS OF THE PRIMARY EFFICACY ENDPOINT(S)

A baseline pain assessment will take place at the first visit (day 0). Pain will then be ascertained daily (including during the "washout" period between the two intervention periods) through a daily pain log kept by participants. The pain logs will be requested from participants at each follow-up visit and at the end of each month in the treatment periods, and data from the pain logs will be compiled and analyzed at the start and end of each of the two treatment periods (on days 0, 90, 120, and 210). Each of these scores will then be entered as raw values for each subject if the parameter distribution is non-normal, ranked values will be used as units of analysis.

The primary endpoint will be change in pain score between baseline and monthly average pain score. The pain score on each day of month one will averaged to obtain the average pain score for month one, and the same will be done

for months two and three, and each of the monthly average scores for resveratrol and placebo periods will be compared to baseline.

In an extreme condition, if a sufficiently large proportion (>30%) of the study subjects experience no pain (a score of 0), zero-inflated negative binomial models will be utilized to analyze the data while considering the individuals that report no pain.

---

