### 4.2.1 PRIMARY ENDPOINT

Self-reported pain will be obtained from all study subjects using the Numeric Pain Rating Scale to score the subject's pain on a 0 to 10 scale. This scale has been validated and widely used. A pain level will be assessed with enrollment in order to assure the participant has pain. An additional assessment will take place at the first visit (day 0). Pain will then be ascertained daily (including during the "washout" period between the two intervention periods) through a daily pain log kept by participants. The pain logs will be requested from participants at each follow-up visit and at the end of each month in the treatment periods, and data from the pain logs will be compiled and analyzed

at the start and end of each of the two treatment periods (on days 0, 90, 120, and 210). Monthly pain averages will be compared to baseline.

The primary endpoint will be change in pain score between baseline and monthly average pain scores. The pain score on each day of month one will be averaged to obtain the average pain score for month one, and the same will be done for months two and three, and each of the monthly average scores for resveratrol and placebo periods will be compared to baseline.

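### The primary hypothesis is resveratrol versus placebo, but the primary-analysis text describes monthly means versus baseline, and no single contrast, month or test level is named as primary

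*Combined protocol and SAP*

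**What the plan says.** **Passages that point to resveratrol versus placebo.**
- The précis asks whether resveratrol "can dampen joint pain for individuals with pseudoachondroplasia compared to placebo (90 days) as measured by daily pain logs".
- Section 10.2 states that "pain (and/or use of pain medication) will be 2.8 points lower on the pain scale (0-10) while on the resveratrol than while on placebo".
- Section 10.1: "The analysis will be performed within the framework of the 2x2 crossover study design".
- Section 10.4.1 plans a multilevel mixed model that takes account of the baseline score, "type of intervention (placebo vs. resveratrol) and the sequence of intervention (placebo first, then resveratrol, or vice versa".

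**Passages that define the primary endpoint and its analysis.**
- Section 4.2.1: "Monthly pain averages will be compared to baseline".
- Section 10.1: "each of the monthly average scores will be compared to baseline". It also says "Median and mean monthly pain will be compared", without saying with what.
- Section 10.4.2: "each of the monthly average scores for resveratrol and placebo periods will be compared to baseline".

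**Related passages.** Section 10.4.2 places the baseline assessment at day 0. It also has the logs analysed at days 0, 90, 120 and 210. Section 10.4.9 answers multiplicity only by saying that the models allow for repeated measurement. The 5% type I error appears only in 10.5, with no sidedness and no link to a test.

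**The concern.** A mean on resveratrol compared with day 0 contains the drug effect plus the placebo response, natural change and regression to the mean. It cannot answer the question in 10.2. Three months on two products give 3 x 2 = 6 such comparisons, and none of them is resveratrol minus placebo.

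The baseline wording may be meant only to form a change score that then enters the 10.4.1 model, but the text does not say so. Even on that reading the plan leaves open which month or summary decides the trial, mean or median, and at what level. That choice could therefore be made with results in view.

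Separately, 10.4.1 lists baseline, treatment and sequence but not period. Sequence and a day-0 baseline are constant within a participant, so neither can remove a period shift from the within-patient contrast.

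**Working it through.** **Inputs from the plan.** n=30 (4.1, 10.5); type I error 5% (10.5), taken as two-sided; SD of the within-patient difference 10-15 and placebo response about 20, both on a 1-100 scale (10.5).

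**Assumptions.** The same SD applies to change from baseline; correlations between monthly contrasts run from 0 to 0.9; a period shift of 5/100. The plan gives none of these.

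**1. The plan's own figure.** The detectable difference for a paired contrast is (1.96 + 0.842) x SD/√n. With SD 10 and n=30 this is 2.802 x 10/5.477 = 5.1, or 5.3 with the t distribution on 28 df. Section 10.5 gives 2.8 for these inputs, which is not reproduced at n=30. At n=100 the formula gives 2.80 (2.83 with t). Section 10.6.1 does say 100 participants, so the two sizes must be reconciled. That is a separate matter. Here 5.3/100 is used as the effect with 80% power at n=30.

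**2. If comparisons with baseline decided success.** Take no drug effect and a fall of 20 on both products. The noncentrality is 20/(SD/√30).
- SD 10: 20/1.826 = 10.95.
- SD 15: 20/2.739 = 7.30.

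Against a critical t of 2.045 (29 df), both give a significant result in more than 99.9% of trials. The resveratrol-minus-placebo contrast on the same simulated data is significant in 5%. With a smaller assumed response of 5/100, resveratrol differs from baseline in 75% (SD 10) or 42% (SD 15) of trials.

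**3. If any one of three monthly treatment contrasts could win.** With independent tests the familywise error is 1 - 0.95³ = 14.3%. Simulated 15/15 crossovers with equally correlated contrasts give:

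| Assumed correlation | Familywise error |
|---|---|
| 0 | 14.4% |
| 0.5 | 12.7% |
| 0.7 | 11.1% |
| 0.9 | 8.6% |

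Large-sample normal draws agree (14.3%, 12.6%, 10.9%, 8.4%), so sample size hardly matters. Modelling the correlation, as 10.4.9 proposes, gives sound standard errors but does not bring these rates to 5%.

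**4. Period omitted (SD 10, shift 5, n=30).** Each patient's resveratrol-minus-placebo difference is moved by +5 in one sequence and -5 in the other.

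- *15/15 split.* The shifts cancel in the mean but inflate the estimated SD to √(100 + 25 x 30/29) = 11.22. The mean must then exceed 2.045 x 11.22/5.477 = 4.19. Its true standard error is still 10/5.477 = 1.826, so power for 5.3 is P(Z > (4.19 - 5.3)/1.826), about 73%. With period in the model it is 80%.
- *Unequal split.* Bias = shift x |n1 - n2|/30. At 18/12 it is 5 x 6/30 = 1.0, with type I error 5%. At 20/10 it is 5 x 10/30 = 1.7, with type I error 10% by simulation; including period returns it to 5%.

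The randomisation method is not stated. Under simple randomisation a 20/10 or worse split has probability 9.9% at n=30. The same 2:1 imbalance has probability 0.09% at n=100.

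**5. Price of including period when there is no shift.** The standard error is (10/2) x √(1/n1 + 1/n2): 1.826 at 15/15, 1.863 at 18/12 and 1.936 at 20/10. Power for 5.3 is 80%, 78% and 75%.

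**The case against.** The strongest case on the other side is that the plan already implies the right test. Its hypothesis is against placebo, 10.1 invokes the crossover and stratifies by drug, and 10.4.1 has a treatment term. Because the endpoint is a change score, comparison with baseline can be read as forming that score. The 10.4.1 text names no month or treatment-by-month term, so read literally it yields one treatment coefficient over all months. This stands, and it makes the harm conditional. It does not fill the gap: 10.4.1 is headed as a general approach and designates nothing as primary.

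Four stronger readings are tempting, and the documents do not support them.
- *The trial will be judged on before-after change.* Sections 10.2 and 10.4.1 argue against this.
- *A win on any month counts.* The plan never says so. It only fails to exclude it, so 8-14% is a what-if figure.
- *Medication use is a second route to success.* The phrase in 10.2 sits beside a result in pain-scale points. Section 7.8 says use is recorded to see whether it falls, but no test of it is described. It is loose wording.
- *The test would be picked after seeing results.* The text supports only that it could be. Section 10.6.1 blinds investigators and analysts, leaving only the coordinator aware of treatment.

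It is also fair that this is a single-site proof-of-concept study, and that the period figures rest on an assumed shift.

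**Conclusion.** The point holds in a conditional form. The plan's hypothesis and its primary-analysis text describe different comparisons, and nothing designates the treatment contrast, a month or summary, or a two-sided 5% level as the primary test. Followed literally, the comparison with baseline cannot answer 10.2: an inert product would pass it almost always under the plan's own placebo response, provided SD 10-15 applies to change from baseline. The familywise figure needs a rule that the plan does not contain.

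The missing period term is a smaller, definite weakness of the 2x2 model. How much it matters depends on the unknown shift and on the split between sequences.

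All sizes use n=30. At the 100 in 10.6.1 the baseline and familywise conclusions are unchanged, and a 2:1 split becomes very unlikely. This should be fixed before unblinding.

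**What to change.** - **10.4.2:** name one within-patient resveratrol-minus-placebo contrast from the mixed model as the single primary test at two-sided 5%. It should be either the 90-day period mean or one pre-specified month, chosen by the sponsor before unblinding. Report changes from baseline descriptively.
- **4.2.1 and 10.1:** make them agree.
- **10.4.1:** add period as a fixed effect, with a random participant effect, and state how the day-120 score is used.
- **10.4.9:** declare other months and median summaries supportive.
- **10.2:** state the primary hypothesis on pain score alone, with medication use supportive.
- **4.1, 10.5 and 10.6.1:** reconcile 30 with 100.

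**Cost.** Wording, one degree of freedom, and no stand-alone claims for the other summaries. With no period shift, power goes from 80% to 78% at 18/12 or 75% at 20/10. No new data are needed.

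**Trade-off in the choice of summary.** The standard error of the three-month mean relative to one month is √((1 + 2ρ)/3), which is 0.816 at ρ=0.5 and 0.966 at ρ=0.9 (assumed correlations). Where one month has 80% power, the 90-day mean has 93% to 83% for a constant effect. If the effect builds evenly to month 3, the mean sees two-thirds of the month-3 effect and has 63% to 49%.
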